1.2 Study design

This is a prospective, randomized, double-blind, placebo-controlled, parallel, multicenter, Phase IIIb study to investigate the safety and efficacy of SZC in patients with hyperkalemia and low bicarbonate (or metabolic acidosis).

The study will be conducted in the United States (US) at approximately 35 investigative sites.

This study consists of a short screening visit (Day 1), an open-label correction period (up to 48 hours), a 4-week randomized treatment period, and a follow-up period (7 days after the last administration of study medication). The total study treatment duration, consisting of open-label and randomized periods, will be 29 days.

Screening will be performed using potassium and bicarbonate value from a study-approved point-of-care test (POCT) to determine eligibility of consenting patients to enter the openlabel correction phase. Patients who meet the POCT eligibility criteria of serum potassium (sK+) between 5.1-5.9 mmol/L inclusive, AND serum bicarbonate between 16-20 mmol/L inclusive, will be enrolled into the open-label correction phase. All baseline parameters should be measured/collected prior to administration of the first dose of study drug in the open-label initial phase.

In the open-label initial phase, patients will receive open-label SZC orally at a dose of 10 g three times daily (TID) for up to 48 hours, depending on POCT potassium value.

Patients who achieve normokalemia (K+ between 3.5 and 5.0 mmol/L inclusive) within 24-48 hours will be randomized 1:1 into the double-blind randomized treatment phase to receive 10 g SZC or placebo once daily (QD) starting dose for the following 28 days. Patients who achieve normokalemia after 24 hours will be randomized and will not need to continue on 10 g SZC TID for another 24 hours.

Study treatment will end with the Day 29 visit, which will be followed by the end of study visit 7 days after the last administration of study medication.

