3 PRIMARY AND SECONDARY VARIABLES

3.1 Time Points and Visit Windows

For all populations, assessments will be assigned to visits and analysis periods for categorical summaries as follows:

- Assessments with missing data and assessments marked "Not Done" will be considered as providing a missing response and are not permitted to be assigned to a visit window.
- The worst value (e.g. out of reference range preferred to within range; abnormal preferred to normal) will be used in each window. If multiple assessments fall within the same window with equal value, then the first non-missing will be used for the summary.

Scheduled day and visit window during the open-label period in Table 1 are with respect to the first dose of open-label study treatment. Baseline is defined as measurements taken at the screening visit on day 1 of the study.

Visit	Scheduled Day of Visit	Analysis Period	Protocol Visit Windows	Visit title in TFLs	Analysis Visit Windows
Visit 1	1	Screening/ Open-Label	Day 1	Visit 1 (Baseline)	Day 1
Visit 2	2	Open-Label	Day 2*	Visit 2	Day 2*
Visit 3	2 or 3	Randomized	Days 2 – 3*	Visit 3 (Randomization)	Days 2 – 3*
Visit 4	8	Randomized	Days 7 – 9	Visit 4	Days 4 – 11
Visit 5	15	Randomized	Days 14 – 16	Visit 5	Days 12 – 18
Visit 6	22	Randomized	Days 21 – 23	Visit 6	Days 19 – 25
Visit 7	29	Randomized	Days $28 - 30$	Visit 7 (EOT)	Days 26 – 32
Visit 8	36	Randomized	Days 33 – 39	Visit 8 (Follow-up)	Days 33 - 39

 Table 1 Definition of visit windows

* Assessments conducted on day 2 and day 3 will be assigned to visit 2 or 3 based on the nominally entered visit on the eCRF.

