3.4.2 Adverse Events

Adverse events (AEs) and Serious adverse events (SAEs) will be collected from start of the open-label correction phase, throughout the treatment period and including during the follow-up period. In addition, SAEs will be recorded from the time of signing the informed consent form and will continue throughout the clinical study until the end of any follow-up prior; this applies even if the subject has not received any study treatment (as per the SOP: Reporting of Individual Safety Events in Clinical Studies). SAEs which occur after the end of the clinical study but with a suspected causal relationship to the IP will be reported by the investigator but will not be included in summary tables and listings.

A treatment emergent AE (TEAE) will be defined as an AE with the start date on or after the first dose date and up to (and including) 7 days after the last dose date or an AE which starts prior to first dose of IP (i.e. before study day 1) which subsequently worsen in severity on or after the date of first dose of IP and up to and including 7 days following the date of last dose of study medication. AEs which occur more than 7 days after the last dose date will only be listed. Similarly, the number of patients experiencing SAEs, AEs that led to withdrawal, AEs that led to death and treatment related AEs, and number of such events, will be summarized by treatment group.

AEs will be further categorized as either occurring during the open-label period, if the start date is on or after the first dose date during the open-label correction period and prior to the date of the first dose of treatment during the randomized placebo-controlled period, or occurring during the randomized placebo-controlled period if the start date is on or after the date of the first dose of treatment during the randomized placebo-controlled period.

The Medical Dictionary for Regulatory Activities (MedDRA) (using the latest or current MedDRA version) will be used to classify AEs system organ class (SOC) and preferred term (PT).

If the relationship to treatment is missing, then the AE will be considered as possibly related to treatment.

Other significant adverse events

An overview of edema-related events (grouped terms include preferred terms of edema, edema peripheral, generalized edema, fluid overload, fluid retention, hypervolemia, localized edema, and peripheral swelling)and instances of sK+ <3.5 will be presented.

Deaths

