4 ANALYSIS METHODS

The principal analyses outlined in this statistical analysis plan will be conducted by Covance Inc., in accordance with the contract with AstraZeneca Pharmaceuticals LP and following the Excellence in Medical Partnership for Outsourced Worldwide Evidence Research (EMPOWER) description of services.

The below mentioned general principles will be followed for analyses:

Descriptive statistics will be used for all variables, as appropriate. Continuous variables will be summarised by the number of observations, mean, standard deviation, median, Q1, Q3, minimum and maximum. Categorical variables will be summarized by frequency counts and percentages for each category.

Unless otherwise stated, percentages will be calculated out of the analysis set total for the treatment group.

For continuous data, the mean and median will be rounded to 1 additional decimal place compared to the original data. The standard deviation will be rounded to 2 additional decimal places compared to the original data. Minimum and maximum will be displayed with the same accuracy as the original data.

For categorical data, percentages will be rounded to 1 decimal place.

SAS® version 9.3 or higher will be used for all analyses

It is acceptable to present large numerical values in more appropriate units. For example, an AUC value of 123,000 ng h/mL may be reported as 123 μ g h/mL instead. It is however, important to keep the units consistent within the report and the precision consistent with that prior to conversion.

In general, for all endpoints the last observation before the first dose of study treatment in the open-label period will be considered the baseline measurement, unless otherwise specified. For assessments on the day of first dose, where time is not captured, a nominal pre-dose indicator, if available, will serve as sufficient evidence that the assessment occurred prior to first dose.

Assessments on the day of the first dose when neither time nor a nominal pre-dose indicator are captured will be considered prior to the first dose if such procedures are required by the protocol to be conducted before first dose.

In all quantitative summaries from baseline, variables will be calculated as the post-treatment value minus the value at baseline. The percentage change from baseline will be calculated as (post-baseline value – baseline value) / baseline value x 100. Absolute and percentage change will be summarized.

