4.2.8 Safety

4.2.8.1 Adverse Events

An overall summary table of the number of subjects experiencing each category of AEs will be produced using the SSO and SSR. Analyses using the SSO will be restricted to AEs which occurred during the open-label correction period and will be presented overall. Analyses using the SSR will include AEs which occurred during the randomized placebo-controlled period and will be presented by treatment group received during the randomized placebo-controlled period and overall.

Any AE occurring within the defined 7-day follow-up period after discontinuation of IP will be included in the AE summaries. Treatment emergent adverse events (TEAEs) occurring prior to first dose of IP (i.e. before study day 1) which subsequently worsen in severity following dosing will be presented in the summary tables.

An overview table will summarize the number and percentage of subjects with at least one of the following AEs, where patients with more than one AE in a particular category are counted only once in that category, as well as the absolute counts of number of AEs. For the overall summary of subjects with any AEs, in the safety set randomized analysis group, the event rate will be displayed. This will be calculated as the Number of subjects with AEs divided by the total number of days at risk for AEs across all subjects in given group, multiplied by 365.25 multiplied by 100.

- Any AEs
- · Any AEs assessed by investigator as possibly related to treatment
- Any AEs with outcome of death
- Any SAEs (including events with outcome of death)
- Any SAEs leading to treatment discontinuation
- Any AEs leading to treatment discontinuation
- Any AEs leading to dose reduction of study treatment
- Any AEs leading to dose interruption of study treatment

• Any AEs leading to study discontinuation

The number and percentage of subjects reporting each AE will be summarized by system organ class (SOC) and preferred term (PT). Tables will be sorted by international order for SOC and PTs will be sorted alphabetically. The following summaries will be produced using the SSO and SSR:

- AEs by SOC and PT;
- Most common AEs (>5% in any treatment group) by SOC and PT;
- AEs assessed by investigator as possibly related to treatment, by SOC and PT;
- AEs by relationship to treatment, by SOC and PT;
- AEs by maximum intensity, by SOC and PT;
- AEs assessed by investigator as possibly related to treatment, by maximum intensity, SOC and PT;

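### Adverse events are split between phases by date alone, so events on the switch day before the first randomized dose drop out of the open-label safety tables

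*SAP*

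**What the plan says.** Section 3.4.2 of the SAP draws the line between phases at a calendar date. An adverse event is open-label if it starts on or after the first open-label dose date and "prior to the date of the first dose of treatment during the randomized placebo-controlled period". It is classed as "occurring during the randomized placebo-controlled period if the start date is on or after the date of the first dose of treatment" in the randomized period. The section gives no onset time, pre-dose indicator or tie-breaker for the switch day.

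Section 4.2.8.1 carries this split into the tables: "Analyses using the SSO will be restricted to AEs which occurred during the open-label correction period and will be presented overall". The SSR tables take the events classed as randomized-period and show them by treatment received.

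On the length of the open-label phase, section 1.2 says that "patients will receive open-label SZC orally at a dose of 10 g three times daily (TID) for up to 48 hours". It adds that "Patients who achieve normokalemia after 24 hours will be randomized" without a further 24 hours of that regimen. Table 1 in section 3.1 puts the randomization visit on Day 2 or 3.

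**The concern.** Splitting phases by date is a common convention and does little harm when a phase lasts weeks. Here the open-label phase lasts one to two days, so the switch day is a large part of it. An event on that day before the first randomized dose happened on open-label SZC only. The rule nevertheless removes it from the SSO, whose stated purpose in section 2.1 is to describe the safety of SZC in the open-label period. The event is then reported under the randomized arm, which may be placebo before any placebo was taken.

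The switch day may also be a day on which events are found. Vital signs, ECG and physical examination are done at randomization (sections 3.4.4 to 3.4.6), and a new or worsening examination finding is reported as an adverse event (section 4.2.8.6). If those assessments come before the randomized dose and the finding is dated that day, the rule moves it to the randomized period.

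What is at stake is mainly the completeness of the open-label safety description.

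**Working it through.** The SAP gives no figure for this point, so there is nothing to reproduce. The check sets the rules side by side and adds simple clock arithmetic.

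**Is there a tie-breaker elsewhere?**

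- Section 3.1 handles same-day order for assessments: "Assessments conducted on day 2 and day 3 will be assigned to visit 2 or 3 based on the nominally entered visit" on the eCRF. It says nothing about adverse events.
- Section 4 allows time of day, or "a nominal pre-dose indicator, if available, will serve as sufficient evidence that the assessment occurred prior to first dose". This concerns baseline before the first open-label dose, not the boundary between phases.
- Section 2.3 ends the open-label period at the date of randomization. That is a different anchor from the first randomized dose, and also a date, so it does not settle order within the day.
- Section 4.2.8.1 lists the study treatment at the time of each event, but the summary tables do not use it.

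No section overrides the date rule.

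**Is a same-day switch plausible?** The SAP does not state that the first randomized dose is taken on the day open-label treatment ends. Section 1.2 gives 28 days of randomized treatment and 29 days of treatment in total, and 29 − 28 = 1 day. With the randomization visit on Day 2 or 3, this makes a same-day switch likely.

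**Share of open-label time moved out of the SSO.** Let s be the clock hour of the first open-label dose and D the open-label duration in hours, with the first randomized dose exactly D hours later. For D = 24 or 48 that dose falls at clock hour s, so s hours of open-label time lie on its date. The share is s/D.

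| First open-label dose (assumed) | D = 24 h | D = 48 h |
|---|---|---|
| 08:00 | 8/24 = 33% | 8/48 = 17% |
| 15:00 | 15/24 = 63% | 15/48 = 31% |

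The durations come from section 1.2. The clock times are assumptions, since the SAP gives none.

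**Share of randomized time at risk.** Take 28 treatment days (section 1.2) plus the 7 days after the last dose during which events count as treatment-emergent (section 3.4.2): 35 × 24 = 840 hours. The misplaced hours are then 8/840 = 1.0% to 15/840 = 1.8% of SSR time at risk.

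**The case against.** The strongest objection is that this is a convention and not a mistake. The SAP does not say whether onset times of adverse events are collected. If only dates exist, any date rule misplaces some switch-day events, and giving the whole day to the open-label phase would take true post-dose events out of the arms. The AE section also uses dates on Day 1, and section 3.4.1 counts exposure in whole days, so the approach is consistent within the plan. This stands in part: a remedy cannot depend on onset time alone. It does not excuse a rule that leaves the switch day out of the SSO altogether in a phase of 24 to 48 hours.

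A reader might infer that the SZC-placebo contrast is materially diluted. The documents do not support that. All patients take the same open-label drug before randomization, so the carried-in events are balanced between arms in expectation. A risk difference is roughly preserved and only a ratio moves slightly towards one. The adverse event tables are descriptive, with no planned between-arm test.

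A reader might also infer that an open-label event rate is understated. Section 4.2.8.1 plans a rate per time at risk only for the randomized safety set; the SSO receives counts and percentages. Nor can one say that every patient randomized after 24 hours has only Day 1 events counted as open-label. The rule is anchored on the first randomized dose, and if that dose is taken the next calendar day, all of Day 2 remains open-label.

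Finally, the listing of treatment at the time of the event lets individual cases be checked, which is practical in a trial that ended early. It does not correct the tables.

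**Conclusion.** The point holds for the open-label safety description. Where the switch falls within one day, the date rule omits pre-dose events of that day from the SSO tables and counts them under SZC or placebo in the SSR tables. Under the assumed start times and a same-day switch, 17% to 63% of open-label time at risk is affected. This is a share of hours; the SAP gives no onset distribution, so the share of events is unknown. For the randomized comparison the consequence is slight, at about 1% to 2% of time at risk. The main reason to act is a complete SSO account, not the protection of a between-arm inference.

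**What to change.** In section 3.4.2, classify events that start on the date of the first randomized dose by onset relative to that dose, wherever an onset time or a pre-/post-dose indicator is available: open-label if before the dose, randomized if at or after it. Where neither is available, keep the event in the SSR tables, count it also in the SSO tables with a flag, and show the SSR overview once without the flagged events.

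The cost is a few lines of SAP text, one derivation and one repeated overview table. The downside is that a few switch-day events without a time appear in the tables of both phases, which a footnote can explain. No study procedure or efficacy analysis changes.

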3.4.3 Laboratory Data

Absolute change from baseline in haematology and clinical chemistry variables will be calculated for each post-dose visit. CTC and maximum post-baseline grade will be calculated at each visit, where appropriate. Absolute values will be compared to the local laboratory reference range and classified as low (below range), normal (within range or on limits of range) and high (above range). All values classified as high or low will be flagged on the listings.

Urinalysis and blood for the determination of clinical chemistry and haematology will be taken at the visits indicated in the Schedule of Activities (SoA) Tables 1 of the CSP. Presentations and summaries will use central laboratory results except for urinalysis dipstick results which will be local. Laboratory parameters include:

Haematology/Haemostasis (whole blood)	Clinical Chemistry (serum)
B-Haemoglobin (Hb)	S-Creatinine (sCr)
B-Leukocyte count	S-Potassium (K+)
B-Leukocyte differential count (absolute count)	S-Bicarbonate (Total CO ₂)
B-Platelet count	S-Chloride (Cl-)
B-Hematocrit (Hct)	S-Glucose
	S-Creatinine
Urinalysis (dipstick, non central)	S-Blood Urea Nitrogen (BUN)
U-Hb/Erythrocytes/Blood	Urea (BUN)/Creatinine Ratio
U-Protein/Albumin	eGFR using the CKD-EPI formula
U-Glucose	Anion gap (blood, from POCT if available)
	S-Albumin
	S-Total Protein
	S-Calcium (Ca++)
	S-Magnesium (Mg++)
	S-Phosphate (PO ₄)
	S-Bilirubin, total
	S-Alkaline phosphatase (ALP)
	S-Alanine amino transferase (ALT)
	S-Aspartate amino transferase (AST)

Table 2: Laboratory Safety Variables

Estimated eGFR will be calculated using the CKD-EPI (chronic kidney disease epidemiology collaboration equation) formula for each time-point and will be analysed as provided by Covance Central Laboratory Services:

eGFR (CKD-EPI)= 141 x min(S_{Cr}/κ , 1)^{α} x max(S_{Cr}/κ , 1)^{-1.209} x 0.993^{Age} x 1.018 [if female] x 1.159 [if Black]

Where S_{Cr} (standardized serum creatinine) = mg/dL, $\kappa = 0.7$ (females) or 0.9 (males), $\alpha = -0.329$ (females) or -0.411 (males), min = indicates the minimum of S_{Cr}/κ or 1, max = indicates the maximum of S_{Cr}/κ or 1 and age = years. eGFR at study entry will be calculated based on either POCT or local laboratory creatinine values.

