4.2.8.3 Laboratory Data

Laboratory data (clinical chemistry, haematology and urinalysis) will be summarized and listed. Laboratory data outside the reference ranges will be indicated in the listings. If a subject has multiple results for a particular test at a particular time point, the first non-missing scheduled value will be used for the summary. System international (SI) units will be reported for all analytes.

Laboratory data absolute and change from baseline values for continuous chemistry, haematology and urinalysis parameters will be summarized at each scheduled assessment time. Separate tables will be provided for the SSO, restricted to visits during the open-label period and presented overall and for the SSR which will include all visits and be presented by treatment received during the randomized placebo-controlled period.

Shift tables will be provided for select tests, where shift from baseline to the maximum value will be summarized. These will be provided separately for the SSO which will be limited to visits during the open-label period and the SSR which will summarize the worst overall value across all visits. Shift tables for laboratory values by worst common toxicity criteria (CTC) grade will be produced for all parameters with grading. These will be provided separately for the SSO which will be limited to visits during the open-label period and be presented overall and the SSR which will summarize the worst CTC grade across all visits and be presented by treatment received during the randomized-withdrawal period.

In addition, the number and percentage of subjects with markedly abnormal clinical laboratory values will be summarized for each parameter by timepoint. These will be provided separately for the SSO, which will be limited to visits during the open-label period and be presented overall, and the SSR, which will summarize abnormal clinical laboratory values across all visits and be presented by treatment received during the randomized placebo-controlled period.

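### SAP section 3.4.3 classifies haematology and chemistry values against the local laboratory range but takes those results from the central laboratory

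*SAP*

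**What the plan says.** Section 3.4.3 opens with the variables it concerns: "Absolute change from baseline in haematology and clinical chemistry variables will be calculated for each post-dose visit". After a sentence on CTC grades, and in the same paragraph, it gives the classification rule: "Absolute values will be compared to the local laboratory reference range and classified as low (below range"), with normal meaning within or on the limits and high meaning above them. It then states the use: "All values classified as high or low will be flagged on the listings".

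The next paragraph names the source of the results: "Presentations and summaries will use central laboratory results except for urinalysis dipstick results which will be local". Table 2 repeats the dipstick exception in its heading, "Urinalysis (dipstick, non central"), and has one further entry that need not be central: "Anion gap (blood, from POCT if available").

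Section 4.2.8.3 returns to the listings and says "Laboratory data outside the reference ranges will be indicated in the listings", without saying whose ranges these are.

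**The concern.** Reference limits are specific to the laboratory and method that generated the number. For haematology and chemistry, the SAP takes the result from one laboratory and the limits from another. A programmer who follows the text would flag central results with limits that do not belong to them. A programmer who departs from it would be making an undocumented choice.

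At stake is the reliability of the high and low flags on the laboratory safety listings. The analytes in Table 2 include potassium and bicarbonate, so their listing flags are covered too.

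**Working it through.** No arithmetic figure is involved, so the check is a comparison of text followed by a statement of when a flag goes wrong.

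**1. Which results does the rule cover?** The classification sentence stands in the paragraph that begins with haematology and clinical chemistry and carries no restriction. Dipstick urinalysis is first mentioned in the following paragraph, so the sentence cannot be read as being about the dipstick alone.

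**2. Where do those results come from, and does the local range fit?**

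| Result | Source in the SAP | Range under 3.4.3 | Fit? |
|---|---|---|---|
| Haematology | Central | Local | No |
| Clinical chemistry other than anion gap | Central | Local | No |
| Blood anion gap | POCT if available | Local | Not clear; the device has its own range |
| Dipstick urinalysis | Local | Not in the sentence's stated scope | A local range would be right |

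**3. Does the SAP use 'local' to mean the laboratory that ran the assay?** Its other uses point the other way. Section 3.3.1 contrasts samples analysed locally on POCT devices with paired samples shipped to the central laboratory. Section 3.4.3 contrasts central results with local dipstick results. It also has eGFR supplied by the central laboratory, but eGFR at study entry based on POCT or local creatinine. No section defines the term differently, and 4.2.8.3 names no laboratory.

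**4. When is a flag wrong?** Write U_C and L_C for the central upper and lower limits, U_L and L_L for the local ones, and x for a central result. Values on a limit count as normal.

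- If U_L < U_C, a result with U_L < x ≤ U_C is flagged high although it is normal by the range that belongs to it.
- If U_L > U_C, a result with U_C < x ≤ U_L should be flagged high and is not.
- If L_L > L_C, a result with L_C ≤ x < L_L is flagged low although it is normal.
- If L_L < L_C, a result with L_L ≤ x < L_C should be flagged low and is not.
- Where the limits coincide, no flag changes.

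The SAP gives neither set of limits, so the number of misflagged values runs from zero upwards and cannot be derived.

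**5. How far does the error travel?**

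- *Listings:* affected. This is the only use of the classes that the SAP states.
- *Categorical summaries by visit:* possible but not stated. Section 3.1 says "The worst value (e.g. out of reference range preferred to within range; abnormal preferred to normal) will be used in each window", which needs a range. For laboratory data, however, 4.2.8.3 has its own rule for several results at one time point: it takes the first non-missing scheduled value.
- *Shift tables:* not shown to depend on it. Section 4.2.8.3 describes shifts from baseline to the maximum value and shifts by worst CTC grade, and does not refer to the 3.4.3 classes.
- *Markedly abnormal values:* 4.2.8.3 does not define these through the 3.4.3 classes.
- *Efficacy, and the overview of low potassium in 3.4.2:* unaffected. They use fixed thresholds, such as sK+ 3.5 to 5.0 mmol/L, a bicarbonate rise of at least 2 or 3 mmol/L, bicarbonate of at least 22 mmol/L, and sK+ below 3.5.

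**The case against.** The strongest defence is that 'local' is loose wording for the range of the laboratory that reported the result, and that the neutral phrase in 4.2.8.3 fits this. If so, nothing would be misflagged. This may well be what was meant, but the text does not say it, and the SAP elsewhere sets local against central. The inconsistency therefore stands whatever the intention.

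A second defence is that the harm is unproven. That is right as to size: only results between differing limits are affected, and no limits are given.

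A reader might also infer more than the document supports:

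- *That every summary is central, or that all flags would be wrong.* Dipstick urinalysis is expressly local, anion gap may come from POCT, and a flag on a central value fails only in the gap between two differing limits.
- *That the ranges of some 35 sites would be applied to one central assay.* Section 1.2 gives approximately 35 sites, but nothing says that site ranges for haematology or chemistry will be collected or used.
- *That the error spreads through the shift tables and the laboratory safety outputs at large, or touches the potassium and bicarbonate endpoints.* The SAP ties the classes only to the listings, and the endpoints rest on fixed thresholds.

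**Conclusion.** Section 3.4.3 is internally inconsistent, and its classification rule is wrong as written for haematology and chemistry results from the central laboratory. Nothing else in the SAP repairs it. The established consequence is possible misflagging on the safety listings, of unknown and perhaps zero extent. An effect on categorical laboratory summaries through section 3.1 is possible but unstated. No efficacy result depends on it. The severity is minor.

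This rests on reading 'local' as the SAP uses it elsewhere, that is, as opposed to central. If the sponsor confirms that the performing laboratory was meant, the point reduces to a correction of wording.

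**What to change.** In 3.4.3, replace the classification sentence with one saying that each result is classified as low, normal or high against the reference range of the laboratory or device that produced it: the central range for central haematology and chemistry, the local range for dipstick urinalysis, and the applicable device range for anion gap taken from POCT. Use the same wording in 4.2.8.3, where the ranges are now unattributed.

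The cost is about one sentence in each section. As far as the SAP shows, no new data collection is needed.
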